6.5 TOXICITY CRITERIA

The following adverse event management guidelines are intended to ensure the safety of each patient while on the study. The descriptions and grading scales found in the revised NCI Common Terminology Criteria for Adverse Events (CTCAE) version 4.0 will be utilized for AE reporting. All appropriate treatment areas should have access to a copy of the CTCAE version 4.0. A copy of the CTCAE version 4.0 can be downloaded from the CTEP web site (http://ctep.cancer.gov/protocolDevelopment/electronic_applications/ctc.htm#ctc_40).

7 NIH REPORTING REQUIREMENTS/DATA AND SAFETY MONITORING PLAN

7.1 **DEFINITIONS**

Please refer to definitions provided in Policy 801: Reporting Research Events found at https://irbo.nih.gov/confluence/pages/viewpage.action?pageId=36241835#Policies&Guidance-800Series-ComplianceandResearchEventReportingRequirements

7.2 OHSRP OFFICE OF COMPLIANCE AND TRAINING / IRB REPORTING

7.2.1 Expedited Reporting

Please refer to the reporting requirements in Policy 801: Reporting Research Events and Policy 802 Non-Compliance Human Subjects Research found at https://irbo.nih.gov/confluence/pages/viewpage.action?pageId=36241835#Policies&Guidance-800Series-ComplianceandResearchEventReportingRequirements.

7.2.2 IRB Requirements for PI Reporting at Continuing Review

Please refer to the reporting requirements in Policy 801: Reporting Research Events found at https://irbo.nih.gov/confluence/pages/viewpage.action?pageId=36241835#Policies&Guidance-800Series-ComplianceandResearchEventReportingRequirements.

Version Date: 07/17/2025 Page 38 of 96

7.2.3 Multi-Institutional Guidelines

7.2.3.1 IRB Approvals

The Administrative PI will provide the NIH Intramural IRB with a copy of the participating institution's approved yearly continuing review. Registration will be halted at any participating institution in which a current continuing approval is not on file at the NIH Intramural IRB.

7.3 NIH REQUIRED DATA AND SAFETY MONITORING PLAN

7.3.1 Principal Investigator/Research Team

The clinical research team will have a teleconference every other week when patients are being actively treated on the trial to discuss each patient. Decisions about dose level enrollment and dose escalation if applicable will be made based on the toxicity data from prior patients.

All data will be collected in a timely manner and reviewed by the Principal investigator or a lead associate investigator. Adverse events will be reported as required above. Any safety concerns, new information that might affect either the ethical and or scientific conduct of the trial, or protocol deviations will be immediately reported to the IRB using eIRB system.

The Principal Investigator will review adverse event and response data on each patient to ensure safety and data accuracy. The Principal investigator will personally conduct or supervise the investigation and provide appropriate delegation of responsibilities to other members of the research staff.

7.3.2 NCI BTTC Coordinating Center Monitoring Plan

This trial will be monitored by personnel employed by Harris Technical Services on contract to the NCI, NIH. Monitors are qualified by training and experience to monitor the progress of clinical trials. Personnel monitoring this study will not be affiliated in any way with the trial conduct.

At least 25% of enrolled patients will be randomly selected and monitored at least biannually or as needed, based on accrual rate. The patients selected will have 100% source document verification done. Additional monitoring activities will include: adherence to protocol specified study eligibility, treatment plans, data collection for safety and efficacy, reporting and time frames of adverse events to the NIH Intramural IRB and FDA, and informed consent requirements. Written reports will be generated in response to the monitoring activities and submitted to the Principal investigator and Clinical Director or Deputy Clinical Director, CCR, NCI.

7.3.3 Safety Monitoring Committee (SMC)

This protocol will require oversight from the Safety Monitoring Committee (SMC). Initial review will occur as soon as possible after the annual NIH Intramural IRB continuing review date. Subsequently, each protocol will be reviewed as close to annually as the quarterly meeting schedule permits or more frequently as may be required by the SMC. For initial and subsequent

Version Date: 07/17/2025 Page 39 of 96

reviews, protocols will not be reviewed if there is no accrual within the review period. Written outcome letters will be generated in response to the monitoring activities and submitted to the Principal investigator and Clinical Director or Deputy Clinical Director, CCR, NCI.

8 SAFETY REPORTING TO BTTC

8.1 **DEFINITIONS**

8.1.1 Adverse Event

Any untoward medical occurrence in a patient or clinical investigation subject administered a pharmaceutical product and which does not necessarily have a causal relationship with this treatment. An adverse event (AE) can therefore be any unfavorable and unintended sign (including an abnormal laboratory finding), symptom, or disease temporally associated with the use of a medicinal (investigational) product, whether or not related to the medicinal (investigational) product (ICH E6 (R2))

8.1.2 Serious Adverse Event (SAE)

An adverse event or suspected adverse reaction is considered serious if in the view of the investigator or the sponsor, it results in any of the following:

- Death,
- A life-threatening adverse event (see **8.1.3**)
- Inpatient hospitalization or prolongation of existing hospitalization
- Persistent or significant incapacity or substantial disruption of the ability to conduct normal life functions
- A congenital anomaly/birth defect.
- Important medical events that may not result in death, be life-threatening, or require hospitalization may be considered a serious adverse drug experience when, based upon appropriate medical judgment, they may jeopardize the patient or subject and may require medical or surgical intervention to prevent one of the outcomes listed in this definition.

8.1.3 Life-threatening

An adverse event or suspected adverse reaction is considered "life-threatening" if, in the view of either the investigator or sponsor, its occurrence places the patient or subject at immediate risk of death. It does not include an adverse event or suspected adverse reaction that, had it occurred in a more severe form, might have caused death. (21CFR312.32)

8.1.4 Severity

The severity of each Adverse Event will be assessed utilizing the CTCAE version 4.0.

8.2 Assessing Causality

Investigators are required to assess whether there is a reasonable possibility that the study agent/s caused or contributed to an adverse event. The following general guidance may be used.

Version Date: 07/17/2025 Page 40 of 96

Yes: If the temporal relationship of the clinical event to the study agent/s administration makes a causal relationship possible, and other drugs, therapeutic interventions or underlying conditions do not provide a sufficient explanation for the observed event.

No: If the temporal relationship of the clinical event to the study agent/s administration makes a causal relationship unlikely, or other drugs, therapeutic interventions or underlying conditions provide a sufficient explanation for the observed event.

8.3 Protocol Specific Definitions

Events not considered to be serious adverse events are hospitalizations for the purposes of this protocol and include:

- Routine treatment or monitoring of the studied indication not associated with any deterioration in condition.
- treatment, which was elective or pre-planned, for a pre-existing condition that did not worsen
- treatment on an emergency, outpatient basis for an event not fulfilling any of the definitions of serious given above and not resulting in hospital admission.

Pregnancy, although not itself a serious adverse event, should also be reported on a serious adverse event form and be followed up to determine outcome, including spontaneous or voluntary termination, details of birth, and the presence or absence of any birth defects or congenital abnormalities.

8.4 Guidelines & Procedures For Reporting Deviations And Unanticipated Problems

Neither the FDA nor the ICH GCP guidelines define the term "protocol deviation." The definition is often left to the Lead Institution IRB. Accordingly, since NCI, Center for Cancer Research is the Coordinating Center and the Administrative PI must adhere to those policies set by the NIH Intramural IRB, the definitions for unanticipated problem and protocol deviation as described in Policy 801 will be applied for reporting purposes for all institutions participating in the NCI Center for Cancer Research Multi-center Project.

Protocol Deviations or Unanticipated problems occurring at a participating institution will be submitted to that institution's own IRB in accordance with local policies and procedures. However, the participating institution must submit a report to the BTTC Coordinating Center even in instances where the local IRB does not require a report.

Deviations or Unanticipated problems must be submitted to the NCI BTTC Coordinating Center within 5 working days after becoming aware of the event (if not reportable to the local IRB). When Deviations or Unanticipated Problems are reported to BTTC, but, the local IRB does not require a report, the report that is submitted to the NCI BTTC Coordinating Center must be accompanied by a formal memo explaining the local policy and the rationale for not reporting the event to the local IRB.

Version Date: 07/17/2025 Page 41 of 96

Deviation or Unanticipated problem Reports and any accompanying documentation (to include the local IRB acknowledgement of the event when applicable) are to be submitted to the NCI BTTC Coordinating Center using the problem report form in Appendix 15.9 via fax at: [contact].

NCI Center for Cancer Research Coordinating Center: Upon receipt of the deviation/unanticipated problem report from the participating institution, the NCI BTTC Coordinating Center will submit the report to the Academic PI for review.

8.5 REPORTING TO THE STUDY DRUG MANUFACTURER (NOVARTIS)

The NCI BTTC Coordinating Center will forward all SAE reports to the lead IRB via the lead investigator, FDA (when applicable), and Novartis:

Novartis Pharmaceuticals Corporation	
[contact]	

SAEs will be forwarded to Novartis via the NCI BTTC Coordinating Center in accordance with the following:

All serious adverse events should be reported to Novartis within 24 hours. In the event of an SAE, the investigator should refer to the Pharmacovigilance section of the contract for reporting procedures. In brief:

The Investigator/Sponsor may report serious adverse drug reactions (SADRs) using either:

An ADEERS form (Adverse Event Expedited Reporting System) available at http://ctep.cancer.gov/reporting/adeers.html

OR

A MedWatch form available at http://www.fda.gov/medwatch/

Occasionally BTTC may contact the reporter for additional information, clarification, or current status of the subject for whom an adverse event was reported.

8.6 GUIDELINES FOR REPORTING SERIOUS ADVERSE EVENTS TO BTTC

What to Report?	When to Report?
All Deaths, except that due to progressive disease, occurring from the time the consent is signed through 30 days after the last day of active treatment	Within 1 working day (24 hours) from the time the research team becomes aware of event

Version Date: 07/17/2025 Page 42 of 96

What to Report?		When to Report?		
A de	ther Serious Unexpected Suspected dverse Reactions (that did not result in eath) occurring from the time the onsent is signed through 30 days after the last day of active treatment	Within 5 working days from the time the research team becomes aware of event		
	Il protocol deviations, non-compliance nd unanticipated problems	Within 5 working days from the time the research team becomes aware of event		
ad or fo in ter pr	regnancy, although not itself a serious diverse event, should also be reported in a serious adverse event form and be followed up to determine outcome, acluding spontaneous or voluntary ermination, details of birth, and the resence or absence of any birth defects it congenital abnormalities.	Within 5 working days from the time the research team becomes aware of event		

The CCR problem report form will be used to submit adverse events to BTTC. See Appendix 15.9. Participating centers must also submit the report to their IRB in accordance with their institutional policies.

The BTTC Coordinating Center will maintain documentation of all Serious Adverse Events from each institution. The BTTC Coordinating Center will notify all investigators of any serious and unexpected adverse experiences that are possibly related to the study agent/s. The investigators are to file a copy with their protocol file and send a copy to their IRB according to their local IRB's policies and procedures.

9 STATISTICAL CONSIDERATIONS

For this study, since there is experience with the drug combination a formal DSMB review will not be necessary.

Time to progression and overall survival will be evaluated using the Kaplan-Meier product-limit survival curve methodology. Six-month Progression Free Survival (PFS) will be estimated using Kaplan-Meier estimates and associated two-sided 95% confidence intervals.

Recurrent glioblastoma with no prior exposure to bevacizumab cohort (Group A): A maximum of 34 patients will be observed in a two-stage Simon optimum design. In the first stage, 9 patients will be accrued. If two or more patients are progression-free at 6 months (PFS6), an additional 25 patients will be accrued. We halt registering patients after 9 patients until we have at least 2 patients are progression free at six months. If 9 or more out of 34 have PFS6, then the study will be declared promising. This study has a 5% chance of declaring promise if the PFS6 rate is at most 15%. It has an 80% chance of declaring promise if the PFS rate is at least 35%.

Recurrent glioblastoma with prior exposure to bevacizumab cohort (Group B): In the group that failed bevacizumab, a maximum of 32 patients will be observed in a two-stage Simon

Version Date: 07/17/2025 Page 43 of 96

optimum design. In the first stage, 14 patients will be accrued. If one or more patients is progression-free at 3 months (PFS3), an additional 18 patients will be accrued. We will halt registration after 14 patients until at least 1 patient is progression free at 3-months. If 2 or more out of 32 have PFS3, then the study will be declared promising. This study has a 5% chance of declaring promise if the PFS3 rate is at most 1%. It has an 80% chance of declaring promise if the PFS rate is at least 12%.

In both patient cohorts, for patients who drop out for reasons other than PD or toxicity, we will replace them. We expect the dropout rate to be not more than 10%, therefore in general it is not an issue to implement the design. The patients who drop out due to toxicity will be counted as treatment failure when implementing the Simon's two stage design and assessing the 6-month PFS rate in either cohort.

The trial will be monitored by the Academic PI, [name], and the study statistician, [name].

We will monitor the toxicity based on the combined data from the above two cohorts with a total sample size of 66. All grade 3 or greater toxicities attributable to the study treatment will be counted. Accrual will be temporarily suspended for analysis after each of the following interim accrual goals. We will monitor the toxicity when the accrual is 5, 10, 20, 35, and 50 based on using the following stopping rule: if the posterior probability of toxicity greater than 0.3 is greater than 0.95 (i.e., Pr (toxicity>0.3|data) >0.95), we terminate the study for toxicity. Assuming the beta prior Beta (0.6, 1.4) for the toxicity, we have the following operating characteristics.

Operating characteristics of the proposed stopping rule

True toxicity probability	0.2	0.3	0.4	0.5
Stopping Probability	1.3%	12.4%	55.0%	92.7%
Average number of patients	65.3	60.3	43.9	24.2
treated				

We obtain the following stopping boundary: the study will be terminated if we observe $\geq 4/5$, 6/10, 10/20, 16/35, 21/50 (# of patients experienced DLTs/# of patients treated). Note that our safety monitoring starts with a small cohort size of 5, and then gradually increases to 15. Therefore, if the treatment agents are overly toxic, the trial will stop before exposing many patients to toxicities.

Patient-reported outcomes: The sample size for this trial was based on the primary endpoint of the study.

Received MDASI-BT forms will be checked versus the timing schedule and considered as valid if they fall within ten days of the scheduled assessment. Compliance rates will be calculated as the number of received valid forms over the number of expected forms. Differences between groups in compliance will be tested by use of Fisher's exact test at every time point.

We will use descriptive statistics to describe how patients rate symptom severity and interference with function at each time point. Error bar graphs for each of the symptoms will be constructed at each time point. The proportion of patients rating their symptoms to be 7 or greater (on a 0-10 scale) will also be reported. We will construct individual patient profiles for each of the selected symptoms to describe the individual patients' patterns of change over time. We will calculate the

Version Date: 07/17/2025 Page 44 of 96

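### The Kaplan-Meier 95% interval planned for the landmark PFS rate collapses when no patient is progression-free, a likely futility result, and no interval is named for Group B's PFS3

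*Combined protocol and SAP*

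**What the plan says.** Section 1.1.1 makes six-month PFS the primary endpoint for Group A (no prior bevacizumab) and three-month PFS the primary endpoint for Group B (prior bevacizumab).

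On estimation, section 9 says: "Six-month Progression Free Survival (PFS) will be estimated using Kaplan-Meier estimates and associated two-sided 95% confidence intervals". It names no variance formula, no scale and no handling of an estimate of zero. The sentence covers six-month PFS only. No interval is stated for PFS3.

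The promising/not promising decision rests on counts, under a Simon optimum design in each group. Group A has 9 patients in stage 1 and at most 34 in all. Its continuation rule is: "If two or more patients are progression-free at 6 months (PFS6), an additional 25 patients will be accrued". Promise then needs at least 9 successes among the 34. Group B has 14 patients in stage 1 and at most 32 in all. Its continuation rule is: "If one or more patients is progression-free at 3 months (PFS3), an additional 18 patients will be accrued". Promise then needs at least 2 successes among the 32.

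Patients who leave for reasons other than progression or toxicity are replaced. Those who leave for toxicity count as failures, both in the Simon rule and in the PFS rate.

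**The concern.** The replacement and failure rules leave few patients censored before the landmark. The Kaplan-Meier estimate is then close to a simple proportion, and its usual standard error is zero or undefined when nobody succeeds. The design makes that a natural result: Group B stops at stage 1 only on 0/14, and Group A can stop on 0/9. Section 1.2.1 itself puts PFS after bevacizumab failure at roughly 0%.

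At stake is the reported precision of the primary rates. An interval of 0% to 0%, or none at all, after 9 or 14 patients would hide how little a small negative cohort rules out.

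**Working it through.** **Inputs (section 9).** Group A: 9 then 25 patients, continue on at least 2/9, promising on at least 9/34, rates 15% and 35%. Group B: 14 then 18 patients, continue on at least 1/14, promising on at least 2/32, rates 1% and 12%. The 5% rate for Group B is an added intermediate value.

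**1. Reproduce the plan's own figures.** P(promising) is the sum, over stage 1 counts that continue, of P(X1 = x) × P(X2 ≥ r − x). Here X1 and X2 are the binomial success counts in stages 1 and 2, and r is 9 (A) or 2 (B).
- Group A: 4.74% at 15% and 81.1% at 35%.
- Group B: 2.87% at 1% and 80.1% at 12%.

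The stated 5% and 80% hold as limits.

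**2. Interval at zero successes.** With no censoring before the landmark, S = x/n = p and the Greenwood variance is p(1 − p)/n.
- Plain scale: SE = √(p(1 − p)/n), which is 0 at p = 0, so the interval is 0% to 0%.
- Log scale: SE of log S = √((1 − p)/(np)), undefined at p = 0.
- Log-log scale: the same quantity divided by |log p|, also undefined.

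The exact (Clopper-Pearson) upper limit at x = 0 is 1 − 0.025^(1/n):
- n = 9: 33.6%, close to Group A's 35% target.
- n = 14: 23.2%, almost twice Group B's 12% target.

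**3. How often this happens.** Going on to stage 2 requires at least one success in either group, so a zero result arises only from the stage 1 stop.
- Group A, (1 − p)^9: 0.85^9 = 23.2%; 0.65^9 = 2.1%.
- Group B, (1 − p)^14: 0.99^14 = 86.9%; 0.95^14 = 48.8%; 0.88^14 = 16.7%.

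**4. Coverage of the nominal 95% interval.** All outcomes were enumerated, including the stage 1 stop. A 0–0 or undefined interval counts as a miss. The Group B rows assume that PFS3 is handled in the same way as PFS6.

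| Group, true rate | Plain | Log | Log-log | Clopper-Pearson |
|---|---|---|---|---|
| A, 15% | 75.6% | 72.1% | 74.8% | 97.9% |
| A, 35% | 82.6% | 92.6% | 94.5% | 94.5% |
| B, 1% | 13.1% | 10.3% | 10.3% | 99.7% |
| B, 5% | 50.8% | 49.3% | 49.3% | 98.0% |
| B, 12% | 79.0% | 80.1% | 82.2% | 98.9% |

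**5. Where the shortfall comes from.** In Group A at 15%, log-log misses 100 − 74.8 = 25.2%, of which 23.2 points are 0/9. In Group B at 12% it misses 17.8%, of which 16.7 points are 0/14. Coverage given at least one success is:

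| Group, true rate | Log-log | Clopper-Pearson |
|---|---|---|
| A, 15% | 97.3% | 97.3% |
| A, 35% | 96.5% | 96.5% |
| B, 1% | 78.1% | 97.4% |
| B, 5% | 96.2% | 96.2% |
| B, 12% | 98.7% | 98.7% |

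The plain scale has a further problem. In Group A at 35% it misses 17.4%: 2.1 points from 0/9, and 9 × 0.35 × 0.65^8 = 10.0 points from a stop at 1/9, where the plain upper limit is only 31.6%.

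**6. Sensitivity to censoring.** A simulation with 10% exponential censoring and exponential PFS (both assumed) moved fixed-sample coverage by about 1 point in Group A and 1 to 5 points in Group B.

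**The case against.** The strongest reply has four parts.

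- **The plan never commits to a poor scale.** This stands. A reader might infer that every reported error bar will be wrong, but section 9 does not support that. On the log-log scale at full fixed sample size, coverage is 94.8% and 95.4% in Group A at 15% and 35%, and 97.2% in Group B at 12%. With the stage 1 stop, log-log equals Clopper-Pearson in Group A at 35%. The choice of scale does not rescue the zero outcome, though.
- **The sentence covers six-month PFS only.** This also stands. The Group B coverage figures describe what follows if the method is carried over to PFS3. If it is not, Group B's primary rate has no planned interval. The same sentence in section 9 would close either gap. The 0/9 case in Group A falls directly under the text as written.
- **The decision does not use the interval.** Correct. A reader might infer that the type I error or power is compromised. It is not: promise is declared on counts, and the stated limits reproduce.
- **An analyst facing 0/14 would probably use an exact limit anyway.** That may be so, and nothing in the documents says a 0–0 interval would be published. But section 9 gives no such rule, and following it literally produces a degenerate interval.

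**Conclusion.** The point holds in a limited form. The planned Kaplan-Meier interval fails when no patient is progression-free, whichever of the three usual scales is chosen. That outcome has probability 23.2% in Group A at its 15% null rate. In Group B it has probability 86.9% at the 1% null rate and 16.7% at the 12% target. The low overall log-log coverage is almost entirely this one outcome. Otherwise log-log is close to exact, except in Group B at 1%, and only the plain scale undercovers more widely. The missing PFS3 interval is a separate gap in the plan.

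The figures assume Greenwood variance, no censoring before the landmark, that a cohort stopped early reports its stage 1 patients, that a degenerate or undefined interval counts as a miss, and, for Group B, that PFS3 is analysed like PFS6. The harm is confined to the reported precision of the primary rates.

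**What to change.** In section 9, state that PFS6 (Group A) and PFS3 (Group B) will each be reported as a landmark proportion with an exact two-sided 95% interval. This can be Clopper-Pearson or an exact interval adjusted for the two-stage design. Plain Clopper-Pearson does not itself account for the stage 1 stop, but it covers 94.5% to 99.7% at the rates tabulated above. Keep the Kaplan-Meier curves as description, with log-log intervals.

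This takes a sentence or two, needs no new data or patients, and leaves the decision rules unchanged. The cost is somewhat wider intervals: at 9/34, 12.9% to 44.4% instead of 13.2% to 41.8% on the log-log scale; at 2/32, 0.8% to 20.8% instead of 1.1% to 18.1%.

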3.7.2 Off Study Criteria

All patients will be followed for overall survival, when possible.

Patients who discontinue treatment due to progression will be followed for survival every 3 months.

Patients who come off therapy for reasons other than progression should be followed until progression or institution of new anti-tumor therapy. They should then be followed for survival.

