6.4.4 Performance Status: Patients will be graded according to Karnofsky Performance Status (See Appendix 15.1). Clinical progression can be declared if there is a decrease in 100 or 90 to 70 or less, at least 20 from 80 or less, or decline in KPS from any baseline to 50 or less, for at least 7 days and not attributable to comorbid events or change in steroid dose.

- 6.4.5 Time to Treatment Failure: From date of registration to the date of first observation of progressive disease (as defined in Section 6.4.1.4.5), non-reversible neurologic progression or permanently increased steroid requirement (applies to stable disease only), death due to any cause, or early discontinuation of treatment.
- 6.4.6 Time to Death: From date of registration to date of death due to any cause.
- 6.4.7 Documenting FLAIR: investigators will be asked to measure tumor related changes on FLAIR sequence as best as possible, as non-enhancing patterns of recurrence can occur. If this occurs within the setting of clinical progression not caused by seizures or other identifiable cause, the patient will be considered to have progressive disease. Please see section 6.4.1 for definition of clinical progression.

Presumed non-enhancing tumor without clinical progression should be observed. The time of progression if eventual clinical deterioration occurs can be back dated to the time of the increase in non-enhancing tumor. Investigators will also be asked to document if recurrence of disease is multifocal.

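### Section 9's toxicity drop-out rule has no landmark limit and names the 6-month rate for both cohorts, so read literally it can fail patients who met their endpoint

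*Combined protocol and SAP*

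**What the plan says.** The primary endpoint is PFS at 6 months for Group A and PFS at 3 months for Group B (Sections 1.1.1, 3.1 and 6.4). Section 9 builds a two-stage Simon rule on each. Group A continues with at least 2 of 9 progression-free at 6 months and is promising with at least 9 of 34. Group B continues with at least 1 of 14 progression-free at 3 months, and "If 2 or more out of 32 have PFS3, then the study will be declared promising".

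Section 9 then gives one drop-out paragraph for both cohorts:

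- Non-toxicity drop-outs: "for patients who drop out for reasons other than PD or toxicity, we will replace them".
- Toxicity drop-outs: "The patients who drop out due to toxicity will be counted as treatment failure", both in the Simon design and when "assessing the 6-month PFS rate in either cohort".

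Neither rule has a time limit, and the term drop out is not defined. Treatment may run up to one year (Sections 3.3.1 and 3.3.2), and unacceptable toxicity ends protocol therapy (Section 3.7.1.3).

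Two other places bear on the point. Section 3.7.2 says "Patients who come off therapy for reasons other than progression should be followed until progression or institution of new anti-tumor therapy". Section 6.4.5 defines a separate measure, Time to Treatment Failure, whose events include "death due to any cause, or early discontinuation of treatment".

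**The concern.** The sentence decides who counts as a success in the go/no-go decision, and it is faulty in two ways.

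1. **Landmark.** A 6-month rate in either cohort does not fit Group B, whose decision is made on 3-month status. A reader who takes the sentence's own 6 months as its time limit would still fail a Group B patient who was progression-free at 3 months and stopped for toxicity in month 5.
2. **Window.** With no limit at all, the same wording reaches a Group A patient who was progression-free at 6 months and stopped for toxicity in month 9.

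Either way, the count would depend on toxicity after the time at which the endpoint is measured. The design rates of 15% against 35% and 1% against 12% are stated as landmark PFS rates, so the stated power would no longer describe the count in use. Group B needs only two successes, so a single recoded patient can matter. The trial is single-arm and open-label, so the choice of window should not be left until results are known.

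**Working it through.** **Inputs (Section 9).** Group A: n1 = 9, continue if ≥2; n = 34, promising if ≥9; rates 15% and 35%. Group B: n1 = 14, continue if ≥1; n = 32, promising if ≥2; rates 1% and 12%. Stated for each: 5% and 80%.

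**Step 1: reproduce the plan.** With X1 and X2 the successes in stages 1 and 2, c1 the stage 1 cut-off and c the final cut-off:

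P(promising) = Σ over x ≥ c1 of P(X1 = x) · P(X2 ≥ c − x).

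For Group B this reduces to P(X1 ≥ 1) − P(X1 = 1)·P(X2 = 0). At 12%: 0.8330 − 0.3188 × 0.1002 = 0.801.

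- Group A: 4.7% at a true rate of 15%, 81.1% at 35%.
- Group B: 2.9% at 1%, 80.1% at 12%.

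A search for the smallest expected sample size under these limits returns exactly the stated designs. They reproduce.

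**Step 2: direction.** Recoding can only turn a success into a failure. At any true rate it can therefore only lower the chance of declaring promise. Power falls and alpha is not inflated.

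**Step 3: size.** Let q be the share of landmark successes later recoded for toxicity. *The documents give no q, so it is an assumption.* The expected overall dropout of at most 10% is not an estimate of it. Two cases:

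- *Both stages:* every success is exposed to recoding before each look, so p is replaced by p(1 − q). Group B at q = 10%: p = 0.12 × 0.9 = 0.108, giving 0.7981 − 0.3422 × 0.1278 = 0.754.
- *Final count only:* stage 1 is judged at rate p. If the trial continues, each success among all n patients is kept with probability 1 − q, and the final cut-off is applied to those kept. This is the milder case. It is realistic, because registration reopens once enough stage 1 patients have reached the landmark, often before a later toxicity stop.

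| Assumed q | A at 35%: both stages | A at 35%: final only | B at 12%: both stages | B at 12%: final only |
|---|---|---|---|---|
| 0 | 81.1% | 81.1% | 80.1% | 80.1% |
| 5% | 76.1% | 77.5% | 77.9% | 78.9% |
| 10% | 70.1% | 72.8% | 75.4% | 77.5% |
| 20% | 55.7% | 60.0% | 69.8% | 73.8% |
| 30% | 38.9% | 43.5% | 63.0% | 68.7% |

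With q = 10% at both stages, the false-positive rate is 2.6% (A) and 2.4% (B). If the sentence is read with an implied 6-month limit, only the Group B columns apply, because no Group A success could then be recoded.

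**Step 4: one-patient reversal in Group B.** One recoded patient changes the final verdict only when the final count is exactly 2. At 12% that has probability 0.3188 × 0.2458 + 0.2826 × 0.1002 = 0.107.

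**The case against.** The strongest reply is that nothing in Section 9 tells anyone to revoke a success already counted. The failure rule applies when implementing the Simon design, and success there is fixed at PFS6 or PFS3. The companion replacement rule has no time limit either. Read just as literally, it would replace a Group A patient who met PFS6 and withdrew in month 9, which is implausible. The natural subject of the paragraph is patients lost before their landmark. This stands as far as it goes: recoding after the landmark is a literal reading, not an explicit instruction. It does not rescue the 6-month wording, which conflicts with Group B's endpoint on any reading.

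Three further objections also stand:

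- q has no basis in the documents, and the both-stages case is the harsher one.
- The error is conservative, so it cannot produce a false promising verdict.
- Counting toxicity stops before the landmark as failures is a defensible, prespecified choice for a single-arm decision.

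On that last point, a reader might infer from Sections 3.7.2 and 6.4.5 that the pre-landmark rule is itself an error, because true progression status is known and discontinuation belongs to a different endpoint. The documents do not support going that far. The study calendar (Section 3.6) marks no MRI at end of treatment or in follow-up, its follow-up footnote covers overall survival only, and progression follow-up may end at new anti-tumor therapy. Landmark status after a toxicity stop may be observed, but it is not secured. Section 9 also already plans a separate Kaplan-Meier estimate of six-month PFS.

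**Conclusion.** The point holds as a wording error in the primary decision rule. The failure sentence has no landmark limit and names a landmark that is not Group B's. Followed as written, even with an implied 6-month limit, it fails a Group B patient who is progression-free at 3 months and stops for toxicity in months 4 to 6. With no limit, it reaches patients in either cohort who stop after their landmark.

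The consequence is lost power only. At an assumed q of 10%, power is 70–73% in Group A and 75–78% in Group B, against 81.1% and 80.1% by design. The Group A figure requires the reading with no limit. These figures show sensitivity and do not predict the loss.

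A reader might infer that the plan orders successes to be recoded, that the Simon designs are miscalculated, or that false positives are at risk. None of these follows: the sentence is ambiguous on timing, the designs reproduce, and alpha can only fall. Severity is moderate. It should be corrected before the primary counts are made, but it does not undermine the design.

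**What to change.** Replace the toxicity sentence in Section 9 with:

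*A patient who stops protocol therapy for toxicity before the cohort's own landmark (6 months in Group A, 3 months in Group B) counts as a failure in the Simon decision and the landmark PFS rate; a toxicity stop after the landmark does not change landmark status.*

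This keeps the conservative rule before the landmark, removes the 6-month wording for Group B, and replaces the undefined term with stopping protocol therapy.

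Optionally, add that the Kaplan-Meier PFS estimate uses observed progression or death status for toxicity stops where it is available, since Section 9 does not say how these patients enter it.

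The cost is one or two sentences, with no added patients, visits or scans and no change to the Simon cut-offs.
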